5.0 Inclusion and Exclusion Criteria/ Study Population

5.a. Study Participants. The study population is adult patients with head and neck cancer undergoing surgery at MUSC with body image disturbance post-treatment.

5.b. Screening for Eligibility. The study team member in collaboration with the electronic medical record and otolaryngology head and neck cancer clinical team, will identify patients ages 18 or older with a pathologic diagnosis of squamous cell carcinoma of the upper aerodigestive tract (oral cavity, oropharynx, hypopharynx, or larynx) or skin of the head and neck presenting for consultation. These patients will be potentially eligible for the study. They will complete a screening BIS questionnaire 1 month after completion of treatment; those with scores ≥ 5 will be eligible for the study. Those with scores < 5 will not be eligible for the study, their BIS questionnaire will be shredded, and no personal information about the patient will be saved. The individual data elements from the clinical records that will be accessed in order to identify potential participants for recruitment include:

1. Name
2. Date of birth, to confirm that potential participant is 18 years or age or older
3. Diagnosis of squamous cell carcinoma of the upper aerodigestive tract or skin of the head and neck.

5.c. Inclusion/Exclusion Criteria:

5.c.1. Inclusion Criteria:

- Pathologic diagnosis of squamous cell carcinoma of the upper aerodigestive tract (oral cavity, oropharynx, hypopharynx, larynx) or cutaneous malignancy of the head and neck (e.g. squamous cell, basal cell, melanoma, etc)
- Age ≥ 18
- American Joint Committee on Cancer (AJCC) stages I-IV
- Curative intent therapy with surgery with or without adjuvant therapy
- BIS score ≥ 5 at 1 month post-treatment

5.c.2. Exclusion criteria:

- Inability to speak English
- Known distant metastatic disease
- Inability or unwillingness of subject or legal guardian/representative to give informed consent

5.d. Inclusion of Women and Minorities. Men and women and members of all races and ethnic groups are eligible for this study.

5.e. Subgroup Distribution: To ensure a reasonable distribution of patients based on potentially relevant characteristics, we will recruit patients diverse by age, race, gender, cancer site, and type of reconstruction.

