8.0 Recruitment Methods

8.a. Recruitment. Potential participants for the study will be identified after their surgery for head and neck cancer. Recruitment will occur primarily at the Head and Neck Cancer Center on the 10th floor of Rutledge Tower. Participants will be identified via a combination of the electronic medical record and otolaryngology head and neck cancer clinical team. The research coordinator who is screening the clinic schedule for patients will determine whether or not the potential trial participant has consented in EPIC to participate in research studies. For patients who have consented in EPIC to participate in research studies will be contacted by the study coordinator for enrollment. For patients who have not consented in EPIC to participate in research studies, the attending physician for the patient will notify the patient of the study.

8.b. Identification of potential participants. The study team member in collaboration with the electronic medical record and otolaryngology head and neck cancer clinical team, will identify patients ages 18 or older with a pathologic diagnosis of squamous cell carcinoma of the upper aerodigestive tract or skin of the head and neck who are undergoing definitive surgical resection. These patients will be potentially eligible for the study. The individual data elements from the clinical records that will be accessed in order to identify potential participants for recruitment include:

1. Name
2. Date of birth, to confirm that potential participant is 18 years or age or older
3. Pathologic diagnosis of squamous cell carcinoma of the upper aerodigestive tract (oral cavity, oropharynx, hypopharynx, larynx) or head and neck skin

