We will call potential participants who have agreed to be contacted about research in EPIC, to discuss the study. For those who have not agreed to be contacted about research in EPIC, we will mail a study recruitment letter prior to their planned clinic visit. If a patient is interested in participating, the coordinator will schedule an in-person meeting to complete screening BIS questionnaire; those with scores ≥ 5 will be eligible for the study. Eligible patients after screening who are still interested in enrolling will complete informed consent paperwork in the clinic using protocols from our previous research. The study participants may include patient's of the PI's, but will not be exclusively patient's of the PIs. For potential participants where the PI is not the attending physician and the potential participant has not consented to participate in research per EPIC, then the attending physician for the patient will introduce the study idea to the potential participant. Other than the notification of the study by the attending physician for potential trial participants, the research team will not ask other clinicians to be involved in recruitment. All of the recruitment will be handled by the study coordinator and team.

8.c. Recruitment Materials. A study recruitment letter will be mailed to potential study participants prior to face-face enrollment and informed consent. A copy of the study recruitment letter has been uploaded into eIRB.

8.d. Participant Compensation. Compensation via checks will be provided to participants for the (n=20 participants). The checks will compensate subjects for time, travel, and enrollment. Participants will receive \$20 for enrollment and \$20 for completion of the study ($\$20 + \$20 = \$40/\text{patient} \times 20 \text{ patients} = \800).

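### Does the squamous-only case-finding wording in 5.b and 8.b conflict with the wider skin-cancer criterion in 5.c.1 enough to need a change?

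*Protocol*

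**What the plan says.** The diagnosis requirement appears in three parts of the Protocol.

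- **5.c.1 (Inclusion Criteria)** takes squamous cell carcinoma of the upper aerodigestive tract and, as a separate alternative, any "cutaneous malignancy of the head and neck (e.g. squamous cell, basal cell, melanoma, etc".
- **5.b (Screening for Eligibility)** has staff look for "squamous cell carcinoma of the upper aerodigestive tract (oral cavity, oropharynx, hypopharynx, or larynx) or skin of the head and neck presenting for consultation". Item 3 of its list of record elements repeats the limit: "Diagnosis of squamous cell carcinoma of the upper aerodigestive tract or skin of the head and neck".
- **8.b (Identification of potential participants)** describes "squamous cell carcinoma of the upper aerodigestive tract or skin of the head and neck who are undergoing definitive surgical resection", and its item 3 reads "Pathologic diagnosis of squamous cell carcinoma of the upper aerodigestive tract (oral cavity, oropharynx, hypopharynx, larynx) or head and neck skin".

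Two general statements carry no histology limit. Section 5.a defines the population as adults having surgery for head and neck cancer at the institution who have body image disturbance after treatment. Section 8.a says: "Potential participants for the study will be identified after their surgery for head and neck cancer".

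The contact step in 8.b follows. Depending on the patient's research consent status in the record system, either "We will call potential participants who have agreed to be contacted about research in EPIC, to discuss the study" or "we will mail a study recruitment letter prior to their planned clinic visit".

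**The concern.** Read literally, the search and the criterion define different groups. In 5.b and 8.b the words about skin complete the phrase that begins with squamous cell carcinoma; they do not stand alone as a diagnosis. A patient with melanoma or basal cell carcinoma of the head and neck meets the diagnosis criterion in 5.c.1 but is not among those the search text describes.

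The search text also has a working role. Section 5.b sends the patients it describes to the screening Body Image Scale (BIS), and a score of at least 5 is itself an inclusion criterion. The contact step in 8.b acts on potential participants, who can be taken to be the group just described. A coordinator working from 8.b might therefore never approach an eligible patient, whereas one working from 5.c.1 or 8.a would. With only 20 subjects planned, each is 5% of the sample (1/20), so the diagnosis definition in use matters for describing who was studied.

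**Working it through.** The question is mainly one of wording, so the check compares the groups defined.

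**Step 1. Coverage.** Section 5.c.1 names 3 skin histologies: squamous cell, basal cell and melanoma. The search phrase covers 1 of them, so 3 − 1 = 2 are outside it, together with anything non-squamous under the open-ended end of the list. This counts examples, not patients. The narrow wording is one phrase used in 2 sections, each time in the running text and in item 3 (2 × 2 = 4 places). These are not four independent rules.

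**Step 2. Direction of the mismatch.** Write E for the diagnoses admitted by 5.c.1 and S for those named in 5.b and 8.b.

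- E = squamous cell carcinoma of the aerodigestive tract, or any skin malignancy of the head and neck.
- S = squamous cell carcinoma of the aerodigestive tract, or squamous cell carcinoma of head and neck skin.

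Every member of S is in E. Using S as the search list can leave eligible patients unapproached, but it cannot admit a patient whose diagnosis is ineligible.

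**Step 3. Which text decides enrolment.** Section 5.c.1 is the list of criteria. Sections 5.b and 8.b say that the patients they describe are potentially eligible, which is a step before eligibility. Neither says that other diagnoses are ineligible, and 5.c.2 excludes no histology. The record-element lists are introduced as what the accessed data include, which need not be exhaustive.

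**Step 4. Whether another route exists.** Section 8.a uses the same term, potential participants, for people identified after head and neck cancer surgery through the medical record and the clinical team, with no histology limit. The contact step adds none of its own. A non-squamous skin cancer patient can reach the screening questionnaire by that route.

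**Step 5. The plan's numbers.** The accrual projection in 11.b is 35 eligible patients per year × 0.846 × 2/3 = 19.7, which agrees with n = 20. The Protocol does not say which diagnosis definition lies behind the 35 and gives no histology mix, so no accrual effect can be derived. For power, the inputs are n = 20, SD of the BIS difference 3.8, a difference of 2.5 and two-sided alpha 0.05. The noncentrality is (2.5/3.8) × √20 = 2.94 on 19 degrees of freedom, and power is 79.7%, in line with the stated 80% at approximately 2.5. Histology is not an input to that calculation.

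**The case for a change.** The best argument for a change is that the search text is operational. The screening BIS is attached to the patients described in 5.b, and no one can qualify without that score. General wording in 5.a and 8.a does not formally amend specific wording in 5.b and 8.b. Section 12.b.4 defines a protocol deviation as any variance from the protocol, so one could ask whether approaching a melanoma patient departs from 8.b. The correction would also be cheap: four wording edits to widen the search text, or one to narrow 5.c.1.

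Part of this stands. The wordings differ, no grammatical reading removes the difference, and it is unclear whether non-squamous skin cancer patients are to be approached.

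The rest does not carry far. A patient who satisfies 5.c.1 and is noticed through 8.a is enrolled in keeping with the criteria, so the deviation worry is weak. Diverging screening lists are a limited risk, because this is a single-site study (7.b) whose recruitment is handled by the study coordinator and team (8.b). Pathologic diagnosis must be known to apply 5.c.1, so the diagnoses actually enrolled can be described in the report whichever wording was followed. A low cost of editing is no reason in itself when no result or patient protection would improve.

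**Conclusion.** The mismatch is a clerical slip, and no change to the plan follows. The case-finding phrase in 5.b and 8.b is narrower than 5.c.1, leaving 2 of the 3 named skin histologies outside it, but it does not exclude those patients and cannot bring in anyone with an ineligible diagnosis. Under either wording the trial enrols patients who meet the diagnosis criterion and yields the same kind of within-patient pre/post BIS comparison. Harmonising the text would change no stated figure, precision, safety provision or conclusion.

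This rests on two assumptions. The first is that staff treat 5.c.1 as governing eligibility, which is how an inclusion list is normally read. The second is that the report describes the diagnoses enrolled. The number of patients affected remains unknown because the Protocol gives no histology mix.

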6.0 Number of Subjects

It is expected that we will enroll 20 subjects in the study.

7.0 Setting

7.a. Study Setting. The primary setting for the study will be the clinic setting at the Head and Neck Tumor Center in the 10th floor of Rutledge Tower or the Hollings Cancer Center.

7.b. Study Sites. This is a single institution study. The only study site is MUSC.

8.0 Recruitment Methods

8.a. Recruitment. Potential participants for the study will be identified after their surgery for head and neck cancer. Recruitment will occur primarily at the Head and Neck Cancer Center on the 10th floor of Rutledge Tower. Participants will be identified via a combination of the electronic medical record and otolaryngology head and neck cancer clinical team. The research coordinator who is screening the clinic schedule for patients will determine whether or not the potential trial participant has consented in EPIC to participate in research studies. For patients who have consented in EPIC to participate in research studies will be contacted by the study coordinator for enrollment. For patients who have not consented in EPIC to participate in research studies, the attending physician for the patient will notify the patient of the study.

8.b. Identification of potential participants. The study team member in collaboration with the electronic medical record and otolaryngology head and neck cancer clinical team, will identify patients ages 18 or older with a pathologic diagnosis of squamous cell carcinoma of the upper aerodigestive tract or skin of the head and neck who are undergoing definitive surgical resection. These patients will be potentially eligible for the study. The individual data elements from the clinical records that will be accessed in order to identify potential participants for recruitment include:

1. Name
2. Date of birth, to confirm that potential participant is 18 years or age or older
3. Pathologic diagnosis of squamous cell carcinoma of the upper aerodigestive tract (oral cavity, oropharynx, hypopharynx, larynx) or head and neck skin

We will call potential participants who have agreed to be contacted about research in EPIC, to discuss the study. For those who have not agreed to be contacted about research in EPIC, we will mail a study recruitment letter prior to their planned clinic visit. If a patient is interested in participating, the coordinator will schedule an in-person meeting to complete screening BIS questionnaire; those with scores ≥ 5 will be eligible for the study. Eligible patients after screening who are still interested in enrolling will complete informed consent paperwork in the clinic using protocols from our previous research. The study participants may include patient's of the PI's, but will not be exclusively patient's of the PIs. For potential participants where the PI is not the attending physician and the potential participant has not consented to participate in research per EPIC, then the attending physician for the patient will introduce the study idea to the potential participant. Other than the notification of the study by the attending physician for potential trial participants, the research team will not ask other clinicians to be involved in recruitment. All of the recruitment will be handled by the study coordinator and team.

8.c. Recruitment Materials. A study recruitment letter will be mailed to potential study participants prior to face-face enrollment and informed consent. A copy of the study recruitment letter has been uploaded into eIRB.

8.d. Participant Compensation. Compensation via checks will be provided to participants for the (n=20 participants). The checks will compensate subjects for time, travel, and enrollment. Participants will receive \$20 for enrollment and \$20 for completion of the study ($\$20 + \$20 = \$40/\text{patient} \times 20 \text{ patients} = \800).

9.0 Consent Process

Informed consent will be obtained for the study. Those who are interested in enrolling in the study will complete a screening BIS questionnaire. A waiver of written informed consent will be obtained to allow patients to complete the screening BIS questionnaire. Those with scores < 5 will not be eligible for the study, their BIS questionnaire will be shredded, and no personal information about the patient will be saved. Those with $BIS \geq 5$ will be eligible for the study. For those subjects who are eligible and interested in enrolling, we will describe the elements of the informed consent and HIPAA forms and answer any questions. Subjects will have time to read the informed consent and HIPAA documents on their own. Any additional questions will be answered and then patients will be asked to sign informed consent and HIPAA forms. All participants will receive a copy of their informed consent and HIPAA forms for their records. Separate copies of the documents will be stored in the study binder under each patient's section. Copies of these documents have been uploaded into eIRB.

9.a. Method of Obtaining Consent. Informed consent will occur via face-face discussion between one of the study team members designated to perform informed consent and the potential study participant. The PI, co-investigators, collaborators, and study coordinator will be authorized to obtain informed consent.

9.b. Location of Informed Consent Process. The informed consent process will take place in a private room in the 10th floor Rutledge Tower Head and Neck Cancer Clinic or in Hollings Cancer Center

9.c. Consenting Parties. Only the study participant will provide informed consent. If the participant is not able to consent, the legally authorized representative [LAR] will provide informed consent (and appropriate documentation to substantiate the LAR will be uploaded or verified in EPIC).

9.d. Waiting Period for Informed Consent. Subjects will be allowed up to one month to decide whether or not to participate in the study.

9.e. Coercion and Vulnerable Populations. To prevent coercion, it will be clearly explained to potential participants that participation in the study is completely optional and failure to participate in the study will not adversely affect their clinical care. Only adults will be enrolled in the study. No cognitively impaired adults will be enrolled in the study. Patients who do not wish to participate will not be consented and no identifying information will be collected from them. The document containing their names (previously prepared to permit identification as mentioned above) will be destroyed immediately if they choose to not participate.

10.0 Study Design / Methods

10.a. Study Design. The proposed study is a prospective, single institution, single-arm, phase II pilot study. Cognitive Behavioral Therapy will be implemented into the clinical care of HNC patients at MUSC and HCC. The effects of CBT on body image disturbance will be measured using the Body Image Scale and analyzed using a pre- and post- study design.

10.b. Study Intervention

10.b.1. Development of a CBT Module for HNC Patients with BID. Although extensive literature exists for implementation of disorder-specific CBT³⁹, no specific CBT modules for HNC patients with BID exist. Therefore a critical initial step is to establish a disorder-specific CBT intervention for HNC patients with BID. In conjunction with [name], [name] will develop a 5-week, CBT module for HNC patients with BID using CBT core components (i.e. psychoeducation, self-monitoring, and cognitive restructuring). The intervention will be informed by existing CBT from other body image disorder realms^{40,41}. The intervention will contain population-specific components including identifying and modifying maladaptive beliefs about disfigurement and functional changes following surgery. It will address the multidimensional nature of BID in HNC patients⁶ and will seek to reduce avoidance behaviors, improve social support, and enhance adaptive stress management skills.

10.b.2. CBT Intervention and Implementation. At the 1-month post-HNC treatment time point, patients with BID as determined by BIS score ≥ 5 will undergo time-limited CBT consisting of 5 weekly sessions. Each session will be guided by the HNC BID module that we develop, but customized to each patient's specific concerns⁴⁰. Each session will last ~60 minutes and be conducted one-one with [name], who will administer the CBT as part of clinical psycho-oncology care at HCC. Patients will complete questionnaires prior to CBT and 1 and 3 months after CBT (**Figure 3**). We considered alternate dose schedules of CBT but chose a 5-week schedule because evidence suggests that brief (e.g. 5-week) CBT reduces anxiety and depression and improves QOL in cancer patients⁵⁸. To overcome the expected travel distance-related barrier to receipt of CBT, we will offer the option of home-based, telemedicine CBT through an existing MUSC program⁵⁹. This will consist of one CBT session at HCC followed by iPad-based, tele-CBT for the next 4 sessions. Patients will receive the iPad and brief training session from MUSC Center for Telehealth staff at the in-person CBT session. They will take the iPads home, use them for the next 4 tele-CBT sessions, and mail them back to MUSC at the study conclusion.

10.b.3. Standardization and Treatment Fidelity. Standardization of intervention administration is critical for study validity and reproducibility. All CBT will be delivered by one psycho-oncologist (SM) with standardized content (regardless of whether the modality is in-person or tele-health CBT). To ensure fidelity of the intervention, the study psycho-oncologist will keep an intervention tracking log which captures data fields such as patient attendance at the session, CBT content delivered, completion of patient homework, technical problems with the session, rating of session length, patient engagement, and patient comprehension (to be completed by psycho-oncologist), and session duration,

10.c. Study Variables

10.c.1 Antecedent Variables.

10.c.1.a Sociodemographics and Oncologic Details. Race, ethnicity, age, gender, marital status, living situation, educational attainment, employment, income level, health insurance, tobacco use, and alcohol consumption will be obtained using questions from the Behavioral Risk Factor Surveillance Survey⁷⁰. Severity of comorbidity will be determined by the Adult Comorbidity Evaluation-27 (ACE-27)⁷¹. Oncologic and treatment data will be prospectively gathered from the EMR using study-specific questionnaires (date of diagnosis and treatment, tumor site, clinical and pathologic AJCC TNM classification and overall stage grouping, surgery, radiation, and/or systemic therapy treatment details, presence/absence of tracheostomy/laryngectomy, enteral feeding tube, patterns of recurrence, survival, and new primaries).

10.c.1.b. Shame and Stigma. Shame and Stigma Scale is a 20-item, validated tool that measures shame with appearance, stigma, regret, and social/speech concerns in patients with HNC⁶⁴.

10.c.1.c. Depression and Anxiety. PROMIS measures of depression and anxiety will be employed. PROMIS measures are validated questionnaire developed by the NIH for evaluating health-related quality of life⁶⁵.

10.c.1.d. Social Roles and Isolation. Social roles and isolation will be assessed by PROMIS measures⁶⁵.

10.c.1.e. Head and Neck Performance Status and Function. Performance Status Scale for Head & Neck Cancer, which assesses performance in domains of eating, speech, and diet⁶⁶.

10.c.2. Outcome Measures

10.c.2.a Primary Outcome Measures.

10.c.2.a.1. Body Image Disturbance. The primary outcome measure will be BID as measured by the Body Image Scale (BIS). The BIS has been validated in oncology patients¹³ and is the most widely used scale for BID in oncology⁶. It is a 10-item measure that is scored on a 4-point Likert scale; higher scores indicate greater body image dissatisfaction. It addresses the affective, cognitive, and emotional aspects of body image⁶⁰. A limitation of the BIS as an outcome measure for studies of BID in oncology patients is that there is no validated, clinically meaningful difference in scale scores. This is despite its use in prior studies attempting to characterize the magnitude and prevalence of body image disturbance as a problem in these patients^{21,72}.

10.c.2.b. Secondary Outcome Measures.

10.c.2.b.1. Body Image Investment. Body image investment (i.e. the importance and influence of appearance) will be measured using the ASI-R⁶¹. This 20-item measure is scored using a 5-point Likert scale with greater scores indicating greater body image investment

10.c.2.b.2. Body Image Coping. The BICSI is a validated measure used to assess cognitive and behavioral responses to manage threats to body image⁶².

10.c.2.b.3. HNC QOL. We will employ the EORTC QLCC30/H&N35 module to evaluate QOL⁶³.

10.c.2.c. Exploratory Outcome Measures.

[figure not shown]
10.c.2.c.1. Caregiver/Dyad CBT Feasibility Data. We will collect these data for use in future studies based on prior work exploring couples-based CBT in breast cancer patients with BID⁶⁷.

10.c.2.c.2. Qualitative Assessment of Experience with BID and CBT. To better understand the patient experiences with BID not captured in the questionnaires as well as their experiences with CBT, we will perform semi-structured exit interviews. Qualitative methods are essential to allow in-depth exploration of patient experiences⁶⁸ and guide intervention development for future studies⁶⁹. Participants will be asked to 1) discuss their preferences about the timing, format and content of the CBT sessions and 2) describe their program experiences and offer recommendations to improve delivery.

10.d. Data Collection:

10.d.1. Data Collection Timeline. The timeline for data collection is shown in **Figure 3**. We have protocols from our ongoing research to obtain data when study time points do not coincide with clinical care.

10.d.2. Data Collection Instruments. The self-administered PRO measures will be completed by patients electronically using an iPad (or paper format if requested) with assistance from the trained program coordinator as needed. A trained program coordinator will assist with data collection instead of a treating physician to minimize social desirability or attention seeking bias⁷³. The data instruments are uploaded into eIRB.

[figure not shown]
